data, including Medicare claims. Brandeis has a long standing relationship with the Center for Medicaid and Medicare Services and houses a large volume of administrative claims that are used for a variety of evaluation and development activities.

We will not be recruiting a control group, but selecting a matched group of participants from the Boston RISE cohort study as controls for aim 1, which focuses on functional outcome measures. The Boston RISE cohort study is a longitudinal cohort study evaluating mobility decline among older primary care patients. Boston RISE contains all of the primary and secondary outcome measures of the study. For outcomes utilizing Medicare Claims data, data is only available for a geographic region encompassing a minimum of 250,000 individuals. Thus, for aims 2 and 3, our collaborators at Brandeis will also identify a second matched control group based upon scientifically relevant data elements, such as age, gender, race, chronic conditions, etc.

VI. BIOSTATISTICAL ANALYSIS

This quasi-experimental study will use a difference-in-difference (D-in-D) approach to assess the impact of mHealth supported PT compared to treatment as usual. We will use a strong matching algorithm, such as exact matching on age, sex and the propensity to participate in treatment, to ensure comparability on observable characteristics between treatments and control group members. For this study the propensity score serves as a form of data reduction, taking many diagnostic flags and reducing them to a single covariate. The basic model estimates the effect of treatment on the change in outcome between baseline and follow-up: $y_{it} = \beta_0 + \beta_1 treatment_i + \beta_2 post_{it} + \beta_3 treatment_i * post_{it} + \gamma controls_{it} + \alpha_i + \varepsilon_{it}$ where y_{it} is cost, $\gamma controls_{it}$ are patient socio-demographic characteristics and $treatment_i$ is a 0/1 variable indicating treatment status. β_3 is the parameter of interest, capturing the joint effect of being in the treatment group at time 2. For the first study object, this model can be extended to include repeated measures of functional status over time. This is a proof of concept pilot study and thus we may not be powered to observe statistically significant differences among our outcomes between groups. However, the effect sizes will be utilized to inform the design of larger trials. For example, meaningful differences in the LLFDI have been published by our group and will help interpret the magnitude of treatment effects observed.

VII. RISKS AND DISCOMFORTS

Common risks and discomforts

All of the proposed measures have been validated among older adults of varying health status. The staff has extensive experience conducting these measures safely among older adults with mobility problems. Many of the assessments for this study involve minimal risk to the participants such as questionnaires, measures of leg strength and power using a double leg press machine, measurement of core muscle weakness, performance of simple balance testing, standing up from a chair, walking eight feet, and balancing with feet in a tandem position. Thus the risks are expected to be similar to those risks involved in participating in a physical therapy program, standing, stair climbing, walking, and activities of daily living. The balance and walk tests could potentially result in a fall, but the protocol includes careful personal monitoring during the

REACH (Rehabilitation Enhancing Aging through Connected Health): Detailed Protocol

testing. Lastly, there is the rare possibility that the Long Distance Corridor Walk could precipitate cardiovascular symptoms. A research assistant (RA) will prepare the course, provide instructions and walk with the participant. In addition, the RA will take vitals before and after the test. Testing may be terminated if participants exhibit significant physical symptoms of shortness of breath, angina, feeling faint or leg pain during or after the test. This test has been used successfully in the context we propose in many population-based studies of older adults as well as the aforementioned LIFE study¹¹

Risks and discomforts related to the exercise intervention include muscle soreness associated with resistance training. This is a natural, expected phenomenon that occurs with rehabilitative exercise, particularly when a person has been inactive for a period of time. This type of soreness is expected to be transient. Other risks and discomforts include the possibility of muscle strain associated with improper technique or attempting to work with a resistance that is not appropriate. As with any physical activity, there is a risk of a cardiovascular event, such as abnormal blood pressure, fainting, irregular heartbeat, or cardiac ischemia and heart attack.

Uncommon risks and discomforts

The criteria for discontinuing a subject's participation include the subject's request, as well as any life-threatening or potentially disabling event. Examples of these events include syncope, an injurious non-accidental fall, hemodynamic collapse, stroke, transient ischemic attack, dysrhythmia, angina, myocardial infarction or hospitalization for acute illness. The risk for these adverse events is very low and no different than what would be encountered in standard outpatient geriatric rehabilitative care. The BU and SCOC sites care for older adults on a daily basis and the therapists employing care as part of the study are very experienced clinicians. Consistent with standard operating procedures for safety, if the participant experiences an acute life-threatening event, they will be initially assessed by the study PT and if immediate urgent care is required 911 will be contacted. Any chronic, or non-life threatening event will be discussed with the Principal Investigator, a Physiatrist with expertise in Geriatric Rehabilitative Care who is either on site or reachable by phone. Additionally, we will have a study safety officer. This will be a clinician with Geriatric expertise that will adjudicate the safety for continued participation of any individual experiencing an adverse event. All events will be recorded and included in the database and reported to the IRB. Any participant who develops adverse events during the conduct of study protocols will be given immediate medical care under the direction of the PI. They will be referred to their primary care physician for ongoing care. It is also possible that the Safety Officer and PCP will decide a participant should temporarily stop participation rather than withdraw. In such cases, the PCP will need to grant clearance following recovery from illness/injury and prior to participants resuming their participation in the study.

VIII. POTENTIAL BENEFITS

Participants may experience the benefits of rehabilitative care and regular exercise. These benefits may include: improvements in muscular strength/power, postural stability, flexibility and endurance and therefore activities of daily living that utilize these attributes. In addition, participants may experience positive psychological benefits of exercise and increased physical activity such as mood enhancement, stress

REACH (Rehabilitation Enhancing Aging through Connected Health): Detailed Protocol

reduction, and increased self-confidence. Lastly, participants might develop a habit of regular exercise that would produce health benefits long after study completion.

The results of this project will have great relevance for the care of older adults. The project has the potential to inform several fields within healthcare, including: primary care, rehabilitative care and health services research. The research may improve the prevention and treatment of mobility decline in older adults, which in turn, may decrease healthcare costs at large.

IX. MONITORING AND QUALITY ASSURANCE

Research staff and physical therapists will be required to demonstrate competence in performing data collection. Training will be based on standardized materials developed for the study. Training will be provided by the PI and his lab manager who have experience in conducting all proposed study measures. Under the supervision of the Principal Investigator and the Research Coordinator, study staff will assess all data collection forms for completeness and accuracy as well as protocol compliance on a weekly basis. Data will be entered directly into and stored within a password protected, HIPAA compliant web-based application hosted by Partners HealthCare Research Computing, Enterprise: REDCap. Each participant will be assigned a study ID number. All data will be coded by study ID only. No personal identifiers will be retained in the outcomes database.

The master list linking ID numbers to subject identifiers will reside in a separate REDCap database. This tracking database will contain patient contact information and will be used to (a) document all contacts with participants from initial scheduling calls, to study visits, through the final follow-up including telephone follow-up; (b) prompt staff to contact participants to schedule follow-up visits (c) generate periodic reports on response rates and success of follow-up contact efforts. Additional study logs tracking communications with participants, study progress and adverse events will also be stored on Syncplicity. Syncplicity is Partners-approved data storage and file sharing system. Only study staff will have access to these files on Syncplicity. We will use Syncplicity to share data with our collaborators at the Center for Neurorehabilitation at Boston University College of Health and Rehabilitation Sciences: Sargent College and the Heller School at Brandeis University.

Exercise videos and communications with research staff via the Wellpepper application will be identified with the same subject ID. Wellpepper runs in a virtual private cloud on Amazon Web Services using MySQL and MongoDB databases. PHI is encrypted on the disk using AES256 encryption. Data is also encrypted over the wire using HTTPS (port 443). Wellpepper, Inc has filed the Vendor Information Security Plan (VISP) with Partners HealthCare. Approval is pending for use of the Wellpepper app for compliance with safety in handling of personal information and compliance with HIPPA regulations. Similarly, Partners Information Systems will prepare all of the iPad minis so that they meet Partner's IS security standards and can be disabled if a device is lost or stolen. Participants will be instructed to utilize cellular data over the course of their study participation and use of Wellpepper. They will be cautioned against less secure networks such as wireless networks that are not password-protected.

REACH (Rehabilitation Enhancing Aging through Connected Health): Detailed Protocol

This consent form will be stored in a locked filing cabinet to which only study staff have the key. Identifying information about a subject will not be used during the discussion, presentation, or publication of any research data.

The Heller School at Brandeis University has developed a comprehensive information security policy and built a secure data network to house sensitive data, including Medicare claims. All data is logged and tracked from the point of arrival to the point of data destruction. We house all original media (which in this case will come from CMS on an encrypted hard drive) with the original files in a locked cabinet. New hard drives are logged in physical media tracking book. A copy of the data files will be placed inside the Heller School secure domain in a folder with limited access (only people who sign the DUA can be given permission to the folder). All analytic files and SAS programs will be stored within the Heller School secure domain. Aggregated results will be exported using a sFTP. All statistical programming and project staff sign a code of personal conduct and agree to follow the rules of the Heller School and the governing DUA (regardless of institution). In the case of CMS paid claims, we cannot take any results out of the secure domain with cell sizes below 12. Both the programmers and site PI, [name], make sure no results that violate this rule are taken outside of the secure domain. When the project is over the original files and aggregate data sets are destroyed using a triple swipe method that has been approved by CMS. The certification of destruction (COD) is sent to CMS and logged in the Heller School DUA tracking system.

The only identifier in the Medicare claims data will be a person level 'link key'. This is a fake ID created for the CMS Chronic Condition Data Warehouse and is different from the beneficiary's Medicare number or Social Security Number. This number is on all claims for the individual. When we destroy the claims data, we destroy the person identifier. There are no other cross-walk files. The only other sensitive information is dates of services.

For CMS projects, data use is governed by the CMS Data Use Agreement (DUA). CMS has a standard DUA that limits the team to the specific project described in the Privacy Board packet. The data cannot be used for any other purpose. The PI of the project is responsible for enforcing this and all other data security requirements.

The Principal Investigator, [name], will be responsible for monitoring the data to ensure participant safety. Participants will be asked to contact study staff with any adverse symptoms. The PI will speak with subjects to make a determination as to the seriousness and nature of the event and what appropriate treatment should include. Study staff will discuss participant safety and any issues that arise at weekly meetings with the PI and our collaborators at BU, or more frequently as needed. [name] will review the safety and progress of the study with collaborators on a monthly basis.

Safety monitoring procedures will also be reviewed by a Safety Officer (SO). The SO will review the study protocol and safety-monitoring plan with all study staff prior to the start of the study. The SO will subsequently meet with study staff as needed to review standardized reports addressing subject symptoms and deviations from the study protocol. Biannual meetings will be organized with the SO to review the

REACH (Rehabilitation Enhancing Aging through Connected Health): Detailed Protocol

progress of recruitment and retention of subjects, compliance with the protocol, and operating procedures with study staff.

The Safety officer will be [name], PhD, a clinician researcher with expertise in geriatrics and primary care and credentialed within the Partners Healthcare System. She will be readily accessible for urgent consultation, since she is from the local area.

The study staff, upon discovery, will review adverse events in keeping with Partners Human Research Policies. All adverse events/serious adverse events will be reported to the IRB by telephone and in writing according to PHS guidelines. Standardized adverse event monitoring forms will be completed. Non-serious adverse events will be continually tracked and included in the annual report to the IRB.

REACH (Rehabilitation Enhancing Aging through Connected Health): Detailed Protocol

X. REFERENCES

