The proposed pilot study will evaluate the benefit of this care program on physical function and health care utilization. The resulting findings have the potential to change how mobility care is provided and thus to prevent mobility decline in older adults and broadly impact national healthcare reform initiatives.

II. SPECIFIC AIMS

For older adults, a decline in mobility skills is a signal event, identifying higher risk for disability and increased healthcare utilization. Based upon the collective research and clinical experience of our multidisciplinary team, we are proposing an innovative rehabilitative care program for older primary care patients at risk for mobility decline. The program targets newly identified risk factors for mobility decline and utilizes mobile health technology to deliver patient centered care more efficiently. The program is consistent with Medicare funded services, but uses a number of innovations such as mobile health technology to demonstrate the potential for long term benefit. This proof of concept quasi-experimental trial will evaluate the benefit of this unconventional care program on physical function and health care utilization after one year of follow up.

Our project will evaluate three main objectives:

1. In comparison to matched controls derived from the Boston RISE cohort study, we will evaluate the benefit of our mobility care program on **physical function** among 76 older adults at risk for mobility decline after one year of follow up.
Hypothesis: In comparison to controls, participants in our mobility care program will have significantly greater improvements in physical function after one year of follow up.
2. In comparison to matched controls derived from Medicare claims data, we will evaluate the impact of our mobility care program on **health care utilization** after one year of follow up.
Hypothesis: In comparison to controls, participants in our mobility care program will have significantly fewer hospitalizations and ED visits after one year of follow up.
3. In comparison to matched controls derived from Medicare claims data, we will evaluate the impact of our mobility care program on **health care costs** after one year of follow up.
Hypothesis: In comparison to controls and after accounting for the estimated per patient costs of our intervention, participants in our mobility care program will have significantly lower healthcare costs after one year of follow up.

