REACH (Rehabilitation Enhancing Aging through Connected Health): Detailed Protocol

III. SUBJECT SELECTION

This proof of concept quasi-experimental pilot study will evaluate the benefit of a novel rehabilitative care program on physical function and health care utilization after one year of follow up. We will recruit 76 community dwelling older adult primary care patients.

Inclusion criteria:

1. Age \geq 65-95 years
2. Able to understand and communicate in English
3. Difficulty or task modification with walking $\frac{1}{2}$ mile (6 blocks) or climbing one flight of stairs
4. Ability to continuously walk 400 m in less than 15 minutes without stopping for more than a minute at a time, sitting, leaning, or the help of another person
5. Lives in a zip code within 10 mile radius of Spaulding Cambridge Facility
6. Baseline Short Physical Performance Battery (SPPB) scores from 3-12 with <20% of SPPB scores in the 11-12 range

Exclusion Criteria:

1. Presence of a terminal disease (e.g. receiving hospice services, metastatic cancer)
2. Major surgery or Myocardial Infarction in the last 6 months
3. Planned major surgery (e.g. joint replacement)
4. Planned move from the Boston area within 1.5 years
5. Mini-mental state exam (MMSE) score <20
6. Major medical problems interfering with safe and successful testing (examples may include: history hip replacement with recurrent dislocation, uncontrolled hypertension, use of supplemental oxygen)

Recruitment procedures will follow the same methodology utilized within the previously IRB approved Boston RISE cohort study.⁷ Prior to contacting any potential participants, [name] and his staff will convene educational sessions with clinicians from participating primary care practices at Mass General Hospital in order to familiarize their staff with the study. To facilitate continued and regular support with recruitment throughout the course of the study, [name] and his research coordinator at MGH primary care are collaborators. They will facilitate recruitment from primary care clinics within the MGH healthcare systems.

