The PCOI loyalty cohort is an IRB approved validated algorithm which identifies and links all patients within MGH primary care practices to a specific primary care provider or, if unable to link to a specific provider, to a specific primary care practice. A list of potentially eligible participants will be generated by the PCOI loyalty cohort and organized by provider. The list will also assign a unique study ID number to each potentially eligible participant. Study staff will provide MGH primary care physicians with a patient list via email or in-person. They will eliminate any of their patients who they do not feel are appropriate for this research study.

Initial contact with subjects will be conducted using identical methods to those of other IRB approved primary care-based studies at MGH. Potential subjects will be sent a letter signed by their primary care physician (PCP) and the Principal Investigator (PI) describing the study and offering them the opportunity to state their disinterest in being contacted. Disinterested individuals can indicate their wishes by checking a box and returning a pre paid postcard or contacting project staff directly. If the potentially eligible primary care patient does not return the postcard or contact us within two weeks of receiving the letter, study staff may contact that individual, asking about their interest in participation. Interested individuals will have their initial eligibility determined through completion of a 1-minute telephone questionnaire designed explicitly for the identification of individuals at risk for mobility decline (those who respond that they have difficulty with or task modification in walking a $\frac{1}{2}$ mile and/or climbing one flight of stairs) and through questions addressing exclusion criteria. If it is felt that a personal visit at the primary care office may increase the likelihood that people will agree to participate, we will arrange to conduct group educational sessions at primary care practices.

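### REACH screens out planned and recent major surgery but the plan does not do so for the Medicare-claims controls, so Aims 2 and 3 are biased in a direction that depends on an unnamed baseline claims window

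*Combined protocol and SAP*

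**What the plan says.** Section III (Subject Selection) lists two exclusions that concern surgery: "Major surgery or Myocardial Infarction in the last 6 months" and "Planned major surgery (e.g. joint replacement". Both are ascertained person by person in REACH. The telephone screen covers eligibility "through questions addressing exclusion criteria", and before that the primary care physicians review the patient lists: "They will eliminate any of their patients who they do not feel are appropriate for this research study".

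Section II (Specific Aims) states the Aim 2 hypothesis as "participants in our mobility care program will have significantly fewer hospitalizations and ED visits after one year of follow up", and the Aim 3 hypothesis, after the cost of the intervention is counted, as "participants in our mobility care program will have significantly lower healthcare costs after one year of follow up". Neither aim separates elective from unplanned admissions.

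For these two aims, section V (Study Procedures) has the claims collaborators "identify a second matched control group based upon scientifically relevant data elements, such as age, gender, race, chronic conditions, etc". Section VI (Biostatistical Analysis) gives exact matching on age, sex and a propensity score that condenses diagnostic flags, followed by a difference-in-difference model. No section applies a REACH exclusion to the claims controls. Section V describes the claims request as the participant's study year plus 6 months of run-out; it names no period before enrolment.

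**The concern.** An operation already planned at entry will often be an admission, with its cost, inside the follow-up year. REACH removes the people who have one; the control pool keeps them. Matching on diagnoses does not separate two people with the same condition when only one is scheduled for surgery. Difference-in-difference removes a stable difference in level between groups, but this selection acts on follow-up alone.

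The look-back exclusion acts on the other period. It takes recent surgical and MI admissions out of REACH's baseline and leaves them in the controls' baseline, so REACH's change over time looks worse.

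The treatment-by-period term therefore mixes any programme effect with two selection effects of opposite sign. Section VI says that the effect sizes from this pilot will inform larger trials, so a distorted estimate does harm even if no test is significant.

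**Working it through.** The plan has no figure to reproduce: the sample of 76 is given without derivation, and no admission, surgery or cost rate is stated. Every rate below is an assumption.

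**Notation**, rates per 100 person-years:
- h, control admissions: 20 to 30.
- Share of these that are elective major surgery: 0.10 to 0.30. So e, the elective major-surgery rate, runs from 20 × 0.10 = 2 to 30 × 0.30 = 9.
- s, the fraction of e removed from REACH follow-up by the planned-surgery exclusion: 0.5 to 1.0.
- m, MI admissions: 0 to 1.

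The rates are taken as stable over time, and a negative shift favours REACH.

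**Follow-up shift** = −e × s. This runs from −2 × 0.5 = −1.0 to −9 × 1.0 = −9.0. Relative to h, that is 0.10 × 0.5 = 5% to 0.30 × 1.0 = 30%. Among 76 people followed for a year it is 0.76 to 6.84 admissions. At an assumed $20,000 to $30,000 per admission, it is 0.010 × 20,000 = $200 to 0.090 × 30,000 = $2,700 per participant.

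**Baseline shift from the look-back.** With a 12-month baseline, half of the year's elective surgery falls in the excluded 6 months, so REACH's baseline falls by 0.5e. With a 6-month baseline, annualised, it falls by e.

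| Claims baseline | Mirrored in controls | Net shift, before MI | Range |
|---|---|---|---|
| None | Neither | −e × s | −1.0 to −9.0 |
| 12 or 6 months | Look-back only | −e × s | −1.0 to −9.0 |
| 12 months | Neither | −e × s + 0.5e | 0 (s = 0.5) to −4.5 (e = 9, s = 1.0) |
| 6 months, annualised | Neither | −e × s + e | +4.5 (e = 9, s = 0.5) to 0 (s = 1.0) |

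In the third row, MI admissions add 0.5m, at most +0.5, so the range becomes +0.5 to −4.5. The largest apparent saving there is 0.045 × 30,000 = $1,350 per participant.

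**A second set of assumptions** tests how far this depends on the inputs: h = 20 to 40, e = 2 to 8, s = 0.25 to 0.8, m = 0 to 1.
- Follow-up only: the shift is −0.5 to −6.4. With no true effect, the rate ratio is (40 − 0.5)/40 = 0.99 to (20 − 6.4)/20 = 0.68. A middle case (h = 30, e = 5, s = 0.5) gives 27.5/30 = 0.92, or 1.9 admissions among 76.
- 12-month baseline, neither mirrored: −e × s + 0.5(e + m) runs from −6.4 + 4.0 = −2.4 to −2.0 + 4.5 = +2.5. It favours REACH only when s exceeds 0.5 × (1 + m/e).
- Chance of a nominally significant false benefit (two-sided 0.05, follow-up only, rates treated as proportions admitted): about 3% to 18% with one control per participant and 3% to 23% with five, against 2.5% without bias. The main harm is to the effect size.

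**The case against.** A reader might infer that REACH would show fewer admissions and lower cost even if the programme did nothing. The documents do not support that as a certainty: the planned estimator is difference-in-difference, the look-back exclusion pulls the other way, and the baseline period is not defined. The table shows shifts in REACH's favour, near zero, and against it.

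Other stronger readings also fail.
- It is tempting to say that all elective admissions are removed from REACH. Only major surgery already planned at screening is; surgery decided on later still counts. The upper end, s = 1.0, is an extreme. REACH also requires mobility difficulty, which is not named among the matching variables and could raise later joint surgery in REACH.
- That claims controls cannot be screened for planned surgery is an inference. The matching list is open-ended, although no element it names records an intention to operate.
- ED visits, part of the Aim 2 outcome, should be little affected by scheduled surgery.
- A reader might conclude that this alone prevents attribution to the programme. Physician screening and volunteering limit attribution in any case, and repairing this point does not remove them.
- Replacing the main outcomes with unplanned admissions and non-elective cost would change the question in section II. That is a debatable trade-off, not something the defect requires.

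The pilot status is a fair reply on significance and power, but not on bias, because the effect sizes are to be reused. The asymmetry itself stands: no section mirrors either exclusion.

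**Conclusion.** The point holds as a bias of uncertain net direction. As written, two REACH exclusions act on the Aim 2 and 3 outcomes in the treated group only, one in follow-up and one at baseline; matching does not address either, and they cancel only by coincidence.

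With no baseline claims, or with only the look-back mirrored, the bias favours REACH by 1.0 to 9.0 admissions per 100 person-years under the first set of assumptions. With a 12-month baseline and neither mirrored, it is about 0 to 4.5 in REACH's favour before MI admissions, and up to 2.5 against REACH under the second set. Mirroring the look-back alone is therefore not enough: it removes the offset and leaves the whole follow-up shift.

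The existence of the asymmetry rests on the text; its size rests entirely on assumed rates.

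**What to change.** 1. Apply the REACH exclusions that claims can show to the control pool at each control's index date, and define that date: major surgery or MI in the prior 6 months, hospice or metastatic cancer, and home oxygen where coded. State in sections V and VI the pre-index claims window that this and the difference-in-difference baseline need, and request it for both groups.
2. Keep all-cause hospitalizations, ED visits and total cost as the stated outcomes. Prespecify a key sensitivity analysis of Aims 2 and 3 that removes elective major-surgery admissions and their costs in both groups and both periods, and limit any claim of benefit to results that hold in it.

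No change to REACH eligibility and no new participants are needed. The costs are extra claims coding, possibly a wider claims request, and fewer events in the sensitivity analysis, which also sets aside any true effect of the programme on elective surgery.

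Section IX bars taking results with cells below 12 out of the secure domain. At the first set of assumed rates, 76 people would have about 15 to 23 admissions (76 × 0.20 to 76 × 0.30), of which about 2 to 7 elective and 11 to 21 not. Where that rule applies, report rates or model estimates, and avoid paired counts that reveal the elective number by subtraction.
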